11.4.3.3 Multiplicity considerations

No adjustment for multiplicity of comparisons was applied for primary or for secondary analyses.

11.4.3.4 Analyses of exploratory endpoints

See [Section 9.4.2](#) for exploratory endpoints details.

- Time to gametocytes clearance
Time to gametocytes clearance will be analyzed using Kaplan-Meier estimators. An overall overview including number of events and cumulative incidence of events with 95% CI will be provided in a summary table, survival curves will be plotted.
- Time to appearance of gametocytes
The first appearance of gametocytes will be presented by time after enrollment for all patients, by treatment arm and separately for each cohort and treatment arm. The denominator for computation of percentages is the mITT population within each treatment arm. Besides, time to gametocytes clearance will be analyzed using Kaplan-Meier estimators in the same way than time to gametocytes clearance.
- Kelch 13 and parasite clearance
Genotype – phenotype associations in the propeller region of Kelch 13 and parasite clearance kinetics (like half-life) will be explored graphically thanks to scatter plots. Linear mixed models may be used to test associations between parasite genotypes and parasite clearance half-lives following OZ439/FQ treatment arm.
- Gametocyte detection RT-PCR (in patients >5 years only)
Standard descriptive statistics will be provided by cohort, treatment arm and time of measurement. If relevant, some correlations or modeling will be explored.
- Phenotypic and genotypic resistance pattern to conventional ACT of *P. falciparum* infecting patients aged >14 years old in Vietnamese sites
Standard descriptive statistics will be provided by cohort, treatment arm and time of measurement. If relevant, some correlations or modeling will be explored.
- In vitro susceptibility testing of *P. falciparum* infecting patients aged >14 years old in Vietnamese sites to OZ439, FQ and both drugs.
Standard descriptive statistics will be provided by cohort, treatment arm and time of measurement. If relevant, some correlations or modeling will be explored.

11.4.4 Analyses of safety data

The summary of safety results will be presented by treatment arm thanks to descriptive statistics (summary tables, graphics) in the following way:

- Summary tables provided separately for “higher NAI” (African patients >5 years) and “lower NAI” populations, and within the “lower NAI” population, separately for African patients ≤ 5 years and Asian patients, by treatment arm, whatever the cohort.
- A summary table provided for “higher NAI population” by treatment arm and by cohort (Cohort 1 & 2).
- A summary table provided for “lower NAI population” by treatment arm and by cohort (Cohort 3 & 4).

No formal inferential testing will be performed.

All the safety analyses will be performed using the safety population.

For all safety data (see [Section 9.2.2.1](#) for details), the observation period will be divided into three phases:

- The pre-treatment phase defined as the time between the patient gives informed consent and the start time of first double-blind IMP administration (excluded).
- The on-treatment phase defined as the start time of first dose of double-blind IMP administration (included) up to Day 63 visit (included).
- The post-treatment phase will be defined as the time after the Day 63 visit (excluded).

For laboratory, vital signs and ECG parameters, Potentially Clinically Significant Abnormalities (PCSAs) will be analyzed using the last available version of PCSA list before database lock.

The following definitions will be applied to laboratory parameters, vital signs and ECG:

- The potentially clinically significant abnormality (PCSA) values are defined as abnormal values considered medically important by the Sponsor according to predefined criteria/thresholds based on literature review and defined by the Sponsor for clinical laboratory tests, vital signs and ECG.
- PCSA criteria will determine which patients had at least 1 PCSA during the on-treatment phase, taking into account all evaluations performed during the on-treatment phase, including unscheduled or repeated evaluations. The number of all such patients will be the numerator for the PCSA percentage.

Baseline safety parameters

The baseline value is defined as the last available value before first double-blind IMP at Visit 1 (Day-1) for laboratory, vital sign and Visit 2 (Day 0 before IMP administration) for ECG parameters. For ECG parameters, baseline will be the mean of the 3 consecutive measures (triplicate) done before dosing.

Baseline definitions specific to each type of safety parameter will be detailed in corresponding sections.

Baseline safety data will be presented along with subsequent safety values assessed during or after dosing.

Drug-induced liver injury

The liver function tests, namely ALT, AST, alkaline phosphatase and total bilirubin, are used to assess possible drug induced liver toxicity. The proportion of patients with PCSA values at any post baseline visit by baseline status will be displayed by treatment arm for each parameter.

A graph of distribution (e-Dish plot) of peak values of ALT versus peak values of total bilirubin will be presented. Note that the ALT and total bilirubin values are presented on a logarithmic

scale. The graph will be divided into 4 quadrants with a vertical line corresponding to 3 x ULN for ALT and a horizontal line corresponding to 2 x ULN for total bilirubin.

The normalization (to ≤ 1 x ULN or return to baseline) of elevated liver function tests will be summarized by categories of elevation (3 x ULN, 5 x ULN, 10 x ULN, 20 x ULN for ALT and AST, 1.5 x ULN for alkaline phosphatase, and 1.5 x ULN and 2 x ULN for total bilirubin), with the following categories of normalization: never normalized, normalized after permanent discontinuation of study drug. Note that a patient will be counted only under the maximum elevation category.

The incidence of liver-related AEs will be summarized by treatment arm. The selection of preferred terms will be based on standardized MedDRA query (SMQ) Hepatic disorder. Time to liver-related treatment discontinuation and time to liver death may also be provided based on hepatic disorder SMQ.

11.4.4.1 Analyses of adverse events

11.4.4.1.1 Definitions

Adverse events will be coded according to the Medical Dictionary for Regulatory Activities (MedDRA, last version available before database lock).

They will be classified into predefined standard categories according to chronological criteria:

- Pre-treatment AEs are defined as AEs that occurred, worsened (according to Investigator opinion) or became serious during the pre-treatment phase
- Treatment emergent AEs (TEAEs) are defined as AEs that occurred or worsened or became serious during the on-treatment phase
- Post-treatment AEs are defined as AEs that occurred worsened or became serious during the post-treatment phase.

11.4.4.1.2 Treatment emergent adverse events

The following frequency tables of TEAEs (incidence tables) will be provided by treatment arm for each population (higher and lower NAI) and separately for each cohort (one table per cohort) during the on-treatment phase:

- Overview of TEAE: Number and percentage of patients with any TEAE, treatment emergent SAE and TEAEs leading to death.
- Summary of TEAEs (number and percentage of patients) by primary system organ class (SOC) (sorted by internationally agreed order), high-level group term (HLGT), high level term (HLT) and preferred term (PT) sorted in alphabetical order for each treatment arm. Multiple occurrences of the same event in the same patient will be counted only once in the tables within a treatment phase. The denominator for computation of percentages is the safety population within each treatment arm.

- Summary of TEAEs (number and percentage of patient s) by primary system organ class (SOC) and preferred term (PT).
- Summary of TEAEs (number and percentage of patient s) by maximal intensity, primary system organ class (SOC) and preferred term (PT).

The following frequency tables of treatment emergent SAEs (incidence tables) will be provided by treatment arm for each population (higher and lower NAI and separately for each cohort (one table per cohort) during the on-treatment phase:

- Summary of treatment emergent SAEs (number and percentage of patients) by primary SOC (sorted by internationally agreed order), HLG, HLT and PT sorted in alphabetical order for each treatment arm.
- Summary of treatment emergent SAEs (number and percentage of patient s) by primary SOC and PT.

Listing of patients presenting treatment emergent SAEs will be provided by treatment arm, patients, primary SOC, PT and onset date and time.

AESIs:

Summary tables of patient count (%) for each AESI (PT or pre-specified grouping) by treatment arm for each population (higher and lower NAI and separately for each cohort (one table per cohort) will be generated:

- Number (%) of patients experiencing torsade de pointes/QT prolongation by Primary SOC and PT.
- Number (%) of patients experiencing hepatic disorders by Primary SOC and PT.

Death:

The following deaths summaries will be generated:

- Number (%) of patients who died by study period (TEAE, on-study, post-study) summarized on the safety population by treatment received.
- Death in nonrandomized patients or randomized and not treated patients.
- TEAE leading to death (death as an outcome on the AE e-CRF page as reported by the Investigator) by primary SOC, HLG, HLT and PT showing number (%) of patients sorted by internationally agreed order of SOC and alphabetic order of HLG, HLT, and PT.

11.4.4.2 Laboratory variables analyses

Baseline definition

The values to be used as baselines will be the values collected on Day -1 for each treatment arm. If any of the scheduled baseline tests are repeated for any patient, the last rechecked values will be

considered as baselines, provided they were done before the start of IMP administration and in the same conditions.

In case of central and local tests performed at the same time, central value will be considered as the baseline value provided it was done before the start of IMP administration. If a central test was not performed but a local value exists at the same date for the same test, the local value will be considered as the baseline.

Abnormalities analyses

For parameters with laboratory ranges and/or abnormality criteria (PCSA), an “on-treatment” analysis will be performed using all post-baseline assessments done during the on-treatment phase, including all unplanned and rechecked values.

Counts of patients with PCSAs at any time during the on-treatment phase will be summarized by treatment arm for each population (higher and lower NAI) and separately for each cohort (one table per cohort) in summary tables showing shifts from normal and abnormal baselines to post-baseline abnormalities. These tables are split by normal/abnormal status and missing value at baseline (if any).

Descriptive statistics and plots

For ALT, AST, ALP, total and conjugated bilirubin, raw data and changes from baseline (including mean, median, quartile (Q1), Q3, standard deviation, minimum and maximum) will be summarized in descriptive statistics, by treatment arm and visit for all patients and separately for each cohort (one table per cohort).

Additionally, time profile plots (mean \pm SD) on raw data and change from baseline will be provided for all patients and separately for each cohort and each of these parameters, using one curve per treatment arm.

Listings

All individual data, for planned hematology and biochemistry including rechecked values, will be listed by biological function, cohort, treatment arm and patient, visit. If any, data from unscheduled laboratory tests will also be listed. In these listings, individual data will be flagged when lower or higher than the lower or upper laboratory limits and/or when reaching the absolute limit of PCSA criteria, when defined. A listing of out-of-normal range definitions will also be provided.

A listing of liver function data for patients experiencing at least one of the following situations will be provided as an in-text table:

- ALT >3 ULN and total bilirubin >2 ULN during the study, with at least one of them being post first dose, irrespective of the definition of the on-treatment phase.
- Direct bilirubin $>35\%$ of total bilirubin and total bilirubin >1.5 ULN, on the same sample post first dose, irrespective of the definition for the on-treatment phase.

A separate listing of individual data from patients with post-baseline PCSAs will be provided.

If any, a listing related to increase in ALT ≥ 2 ULN will be provided, including notably the information on IMP intake, medical and surgical history, alcohol habits, trigger factors, event details with ALT values, associated signs and symptoms.

11.4.4.3 Analyses of vital sign variables

11.4.4.3.1 Heart rate and blood pressure

Heart rate (HR) and systolic and diastolic blood pressure (SBP and DBP) will be analyzed as raw parameter value and change from baseline (for supine position only).

Baseline definition

The values to be used as baseline will be the Day-1 for each treatment arm. If any of the scheduled baseline tests are repeated for any patient, the last rechecked values will be considered as baseline, provided they were done before the start of IMP administration.

Abnormalities analyses

For all parameters, an “on-treatment” analysis will be performed using all post-baseline assessments done during the on-treatment phase, including all unplanned and rechecked values.

Counts of patients with post-baseline PCSAs will be provided in summary tables regardless of the normal or abnormal status of the baseline. This table will be presented by treatment arm for each population (higher and lower NAI) and separately for each cohort (one table per cohort).

Descriptive statistics

For heart rate and blood pressures, raw data and changes from baseline (for supine position only including mean, median, quartile (Q1), Q3, standard deviation, minimum and maximum) will be summarized in descriptive statistics, for each type of measurement and by treatment arm, visit and time of measurement for all patients and separately for each cohort (one table per cohort).

Listings

Individual data for supine position, including unplanned and rechecked values, will be listed by cohort, treatment arm and patient, visit and time of measurement.

In the listings, values will be flagged when reaching the limits of the PCSA criteria, when defined.

A separate listing of individual data from patients with post-baseline PCSAs will be provided.

11.4.4.3.2 Body temperature

Raw data and changes from baseline will be summarized in descriptive statistics, by type of measurement (axillary [recommended], tympanic, oral or rectal), treatment arm, visit and time of measurement for all patients and separately for each cohort (one table per cohort).

11.4.4.4 ECG parameters analyses

For all ECG parameters the mean of the 3 consecutive measures of ECG (triplicates) at each time of measurement when applicable will be calculated for each parameter, patient and nominal time point and will be used for analyses.

Heart rate, PR-, QRS-, and QT-intervals, corrected QTcF (Fridericia) will be analyzed as raw parameter value and change from baseline, as well as percent change from baseline for selected parameters.

Baseline definition

The value to be used as baseline will be defined as the average of the triplicate assessments done on Day 0 T0 for each treatment arm.

Abnormalities analysis

For all parameters, an “on-treatment” analysis will be performed using all post-baseline assessments done during the on-treatment phase, including all unplanned and rechecked values. Counts of patients with post-baseline PCSAs will be provided in summary tables regardless of the normal or abnormal status of the baseline. This table will be presented by treatment arm for each population (higher and lower NAI) and separately for each cohort.

A summary of ECG morphological assessments (for all high level types of comments) will be provided by cohort and treatment arm.

Descriptive statistics and plots

For all parameters, raw data and changes from baseline will be summarized in descriptive statistics, by treatment arm, visit and time of measurement for all patients and separately for each cohort (one table per cohort). Summary plots (mean \pm SD) on raw data and changes from baseline, as well as percent change from baseline for selected parameters will also be generated, separately for each cohort and each of these parameters, using one curve per treatment arm.

Additionally, time profile plots (mean \pm SD) on raw data and change from baseline will be provided on all ECG parameters for all patients and separately for each cohort and each of these parameters, using one curve per treatment arm.

Listings

Individual data, including rechecked values, will be listed by cohort, treatment arm, patient, visit and time of measurement. In the listings, values will be flagged when reaching the limits of the PCSA criteria, when defined. A separate listing of individual data from patients with post-baseline PCSAs will be provided.

11.4.5 Analyses of pharmacokinetic and pharmacodynamic variables

11.4.5.1 Analysis of pharmacokinetic data

Pharmacokinetic analysis for OZ439, FQ and SSR97213 are described in [Section 9.4.1.5](#).

Blood and plasma FQ (respectively its metabolite [SSR97213]) observed concentrations, plasma OZ439 observed concentrations will be summarized by treatment arm and by time point using descriptive statistics for each cohort. Blood/plasma concentration ratio for FQ and SSR97213 will be provided by treatment arm and by time point using descriptive statistics for each cohort. Additional plots will be prepared, as deemed necessary.

Pharmacokinetic parameters of FQ, its metabolite SSR97213 and OZ439 compounds will be summarized by descriptive statistics (such as arithmetic mean, geometric mean, median, SD, SEM, CV, minimum, and maximum) for each treatment arm and each cohort.

The results of population PK modeling will be reported separately from the study report.

11.4.5.2 Analysis of pharmacodynamic data

Not applicable.

11.4.5.3 Analysis of pharmacokinetic/pharmacodynamic data

11.4.5.3.1 Relationship between ACPR and dose or concentrations

For each cohort and for all patients separately, the dose-response association of single-dose OZ439/FQ for PCR-adjusted ACPR will demonstrate how the probability of a response in PCR-adjusted ACPR increases with increasing dose OZ439/FQ thanks to a logistic regression with SAS® PROC LOGISTIC by using ACPR data at Days 28, 42 and 63. Same analysis will be done between PCR-adjusted ACPR and exposure.

Results of logistic regressions of PCR-adjusted ACPR on dose (respectively FQ/SSR97213 blood or OZ439 plasma concentrations) of OZ439/FQ will be provided in a summary table including odds ratio estimates, the corresponding 95% Wald confidence intervals and p-value.

11.4.5.3.2 Relationship between PK concentrations and QTc parameters

Two PK/PD statistical analyses (one for cohort 1a in a first time and then by pooling cohort 1a and 1b in a second time) will be done with ECG parameters (HR, PR, QRS and QTcF) regarding FQ and SSR97213 compounds by combining the two compounds in the same linear direct/indirect model (as covariates or by using the molecular weight formula in order to obtain an “average” concentration). A complementary analysis will be performed pooling Cohort 1a and 1b and including OZ concentrations as PK variable (in addition to FQ and SSR97213). These two analyses will be prepared by a Sponsor’s unblinded independent statistician.

The first PK/QTc analysis will include 30 African patients >14 years (Cohort 1a) receiving the dose levels OZ439/FQ 800/400, 800/600 and 800/900 mg.

The second PK/PD analysis will include a total of 42 African patients >14 years (Cohort 1a & 1b) receiving the dose levels 800/400, 800/600, 800/900 and 800/1200.

Concentrations below the limit of quantification (LOQ LOQ), will be replaced with $\frac{1}{2}$ LOQ in the statistical analyses. LOQ is defined as 1 ng/mL for OZ439 and as 5 ng/mL for FQ and SSR97213.

Relationships between change from baseline in ECG parameters by combining the two compounds FQ and SSR97213, using the molecular weight (MW) 433.77 g.mol⁻¹ for ferroquine 419.74 g.mol⁻¹ for SSR97213 or by using ferroquine and SSR97213 blood drug concentrations as covariates in the same model (selection of the best model will depend of fit statistics criteria), on the restricted time window [Day 0 T_{2h} – Day 2 T_{48h}] will be explored using data from OZ439/FQ:

1st step: 800/400, 800/600 and 800/900 mg dose levels from Cohort 1a.

2nd step: 800/400, 800/600, 800/900 and 800/1200 mg dose levels from Cohorts 1a and 1b. (OZ concentration to be added as PK variable in the complementary analysis with the molecular weight (MW) of 469.28 g.mol⁻¹).

These PK/QTc analyses may or may not be reviewed by the DMC at the same time as the safety data review and therefore may or may not be considered by the DMC for DMC decision rule.

A third PK/PD analysis will include all patients of all cohorts receiving the dose levels 800/400, 800/600, 800/900 mg and/or 800/1200 mg at the end of the study. Relationships between change from baseline in ECG parameters versus FQ (respectively SSR97213 and OZ439) blood drug concentrations, on the restricted time window [Day 0 T_{2h} – Day 2 T_{48h}].

11.4.5.3.3 Exploratory plots

The relationship between change from baseline in HR, PR, QRS and QTcF and FQ (respectively SSR97213 and OZ439 [complementary analysis at end of Cohort 1 and final analysis only]) concentrations, respectively, from Day 0 T_{2h} to Day 2 T_{48h} will be first explored graphically, in order to investigate any potential delayed or sustained effects and the type of PK/PD modelling to be done, using the following plots:

- Plot of Mean (\pm SEM) change from baseline in HR, PR, QRS and QTcF and FQ (respectively SSR97213 and OZ439 [complementary analysis at end of Cohort 1 and final analysis only]) concentrations, versus time (hours post-dose) overlaid onto the same plot; the same plot will be produce on the log concentration;
- Hysteresis plot of individual and mean change from baseline in HR, PR, QRS and QTcF and FQ (respectively SSR97213 and OZ439 [complementary analysis at end of Cohort 1 and final analysis only]) concentrations, respectively;
- Histogram of distribution of time of largest change from baseline in HR, PR, QRS and QTcF and largest FQ (respectively SSR97213 and OZ439 [complementary analysis at end of Cohort 1 and final analysis only]) concentrations, respectively;

- Histogram of distribution of time of smallest change from baseline in HR, PR, QRS and QTcF and largest FQ (respectively SSR97213 and OZ439 [complementary analysis at end of Cohort 1 and final analysis only]) concentrations, respectively.

11.4.5.3.4 Modeling: linear model

A random coefficients linear regression of QTcF (respectively HR, RR) change from baseline vs. concentration will be used from Day 0 T2h to Day 2 T48h, with fixed terms for common intercept and slope, with or without time effect, and with random terms for patient -specific intercept and slope, and using an unstructured variance-covariance structure for random coefficients and a common variance for error, using SAS® PROC MIXED procedure:

Change from baseline QTcF_{ij} = ($\alpha + A_i$) + Time_j + ($\beta + B_i$) × Concentration_{ij} + error,
with i = patient and j = Time

Estimates and 90% CIs of coefficients (intercept corresponding to the mean of individual time Intercept in case of time effect is included in the model and slope) of the linear regression model, and the prediction (estimate and 90% CI) in change from baseline of ECG parameters corresponding to the C_{max} value (geometric mean) for each FQ dose group will be provided for FQ and SSR97213 respectively (OZ439 compound for the complementary analysis at end of Cohort 1 and final analysis only), and will be calculated following the formula $\beta_{\text{estimated}} \times \text{observed geometric mean } C_{\text{max}}$:

- OZ439 800 mg/FQ xxx mg/ at geometric mean of C_{max} for each dose of OZ439/FQ.
- Scatter plots of change from baseline versus FQ and SSR97213 concentrations, respectively, with the regression line overlaid, will also be provided.

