11.4.5.3.5 Model Averaging to Concentration-QT analysis

By combining estimates obtained from several competing models (linear, exponential and Emax), Model averaging (MA) will provide estimators which will have good robustness properties compared to the linear model or non-linear model estimates.

The estimated endpoint will be the drug effect on delta QTcF at the C_{max} value (geometric mean) observed concentrations at the maximal dose (OZ439 800 mg/FQ 1200 mg).

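### When FQ and SSR97213 are separate covariates in the PK/QTc model, the protocol fixes only per-analyte predictions and specifies no joint QTc effect with a 90% CI for each dose group

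*Protocol*

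**What the plan says.** Section 11.4.5.3.2 describes two interim PK/QTc analyses (Cohort 1a, then Cohorts 1a and 1b pooled) that combine FQ and SSR97213 in one model. The two analytes enter "as covariates or by using the molecular weight formula in order to obtain an" average concentration. The first option is worded again as "by using ferroquine and SSR97213 blood drug concentrations as covariates in the same model", and the second as "using the molecular weight (MW) 433.77" g/mol for FQ and 419.74 g/mol for SSR97213. The choice is left open: "selection of the best model will depend of fit statistics criteria". A complementary analysis on the pooled cohorts adds OZ439. For the final analysis of all cohorts, the same section relates ECG change to FQ, SSR97213 and OZ439 respectively.

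Section 11.4.5.3.4 writes a model with a single concentration term. The prediction and its 90% CI at the geometric mean Cmax "for each FQ dose group will be provided for FQ and SSR97213 respectively", and they "will be calculated following the formula" of estimated slope times observed geometric mean Cmax. A bullet then lists the prediction "for each dose of OZ439/FQ" without saying which analyte it refers to or whether effects are summed.

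Two other places touch the same output. The synopsis (analysis of secondary endpoints) promises an estimate and 90% CI at the geometric mean Cmax for each treatment arm. Section 11.4.5.3.5, on model averaging, says: "The estimated endpoint will be the drug effect on delta QTcF at the" geometric mean Cmax of the maximal dose (800/1200 mg). It names no analyte basis and no CI.

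**The concern.** With two analytes as covariates, the modelled drug effect at a given time is b1 x C1 + b2 x C2, plus b3 x C3 when OZ439 is included. The stated output rule has room for one slope and one concentration only. Applied to this model it returns b1 x Cmax1 and b2 x Cmax2 separately. Each describes a patient with one analyte at its peak and the other absent, which does not occur after dosing. The two peaks need not coincide, so adding the products is not the effect at any particular time. The interval for the sum needs the covariance of the slope estimates, which two separate intervals do not carry.

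This is more than detail left to a later plan: the protocol states a formula that does not fit one of the two models it allows. Section 4.1 names QTc prolongation as an identified risk of FQ and OZ439, alone or combined. Section 11.5 has these analyses prepared for the DMC, and Section 7.4.2 places them before Cohort 1b and before Cohort 2. A figure supplied there should describe the regimen rather than one component of it.

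**Working it through.** **1. The protocol's own predictions.** Section 4.2.2 gives predicted placebo-corrected QTcF changes at several FQ Cmax values. Calibrating on the paediatric figure (756 ng/mL: 3.52 ms, 90% upper bound 9.74 ms):

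- slope = 3.52 / 756 = 0.004656 ms per ng/mL
- upper-bound slope = 9.74 / 756 = 0.012884 ms per ng/mL

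| FQ Cmax (ng/mL) | Stated: estimate (upper bound), ms | Slope x Cmax, ms |
|---|---|---|
| 284 | 1.3 (3.7) | 1.32 (3.66) |
| 388 | 1.8 (5.0) | 1.81 (5.00) |
| 618 | 2.9 (8.0) | 2.88 (7.96) |
| 670 | 3.1 (8.6) | 3.12 (8.63) |

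All agree to rounding. The earlier predictions therefore have the form of the Section 11.4.5.3.4 formula: slope times Cmax through the origin, expressed at FQ Cmax alone.

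**2. What the formula yields under each permitted model.**

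- *Combined concentration.* The molecular-weight factor is 433.77 / 419.74 = 1.033. One slope times one combined Cmax is the joint FQ + SSR97213 effect, and its CI follows directly. Section 11.4.5.3.4 does not say, however, that its per-analyte reporting changes in this case.
- *Separate covariates.* The formula gives two partial effects. No section states the sum or its CI for each dose group.

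**3. Illustration of the total.** The protocol gives no SSR97213 slope, SSR97213 Cmax or slope covariance, so these are assumptions.

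- FQ part: 3.52 ms. Reading 9.74 as the upper limit of a two-sided 90% CI, SE = (9.74 - 3.52) / 1.645 = 3.78 ms.
- Metabolite part: a fraction f of the FQ part at the same time point, with the same relative SE.
- rho: correlation of the two slope estimates.
- Total = 3.52 x (1 + f); SE of total = 3.78 x sqrt(1 + f^2 + 2 x rho x f); upper bound = total + 1.645 x SE.

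For f = 0.5 and rho = -0.9: total = 5.28; SE = 3.78 x sqrt(0.35) = 2.24; upper bound = 5.28 + 3.68 = 8.96 ms. For f = 0.5 and rho = 0.5: SE = 3.78 x sqrt(1.75) = 5.00; upper bound = 5.28 + 8.23 = 13.51 ms.

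| f | Total (ms) | Upper bound, rho = -0.9 | rho = 0 | rho = 0.5 | Sum of the two separate upper bounds |
|---|---|---|---|---|---|
| 0.25 | 4.40 | 9.27 | 10.81 | 11.53 | 12.18 |
| 0.5 | 5.28 | 8.96 | 12.23 | 13.51 | 14.61 |
| 1 | 7.04 | 9.82 | 15.84 | 17.81 | 19.48 |

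Within each row the two separate intervals are identical throughout, yet the upper bound of the total moves by 2.3 ms (f = 0.25), 4.6 ms (f = 0.5) and 8.0 ms (f = 1) as rho changes. Two of the nine values lie below the FQ-only bound of 9.74 ms and seven lie above it.

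**The case against.** A reader might infer that the total effect is never produced. The documents do not support that. If the combined concentration is selected, the single slope gives the FQ + SSR97213 total, and the one concentration term written in Section 11.4.5.3.4 suits that form. Section 11.4.5.3.5 plans one drug effect at the 800/1200 mg dose, and the synopsis promises a figure per arm. These places are ambiguous about the analyte basis rather than silent.

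A reader might also infer that every reported number understates the regimen's effect. That needs non-negative slopes in a two-covariate model. With correlated analytes one fitted slope can be negative, and the other product then exceeds the total. In a single-analyte model, a natural reading of the final analysis, the slope absorbs part of the effect of the correlated analytes. The upper bound can also fall: 8.96 against 9.74 ms above. Positively correlated covariates usually give negatively correlated slope estimates, so that direction is realistic.

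Two limits on the consequence also stand. The protocol says repeatedly (Sections 4.2.2, 7.4.2, 11.4.5.3.2 and 11.5) that the DMC may or may not take these analyses into account in its decision rule. The safety review includes ECG abnormalities observed under the full regimen (Section 6.1), and Section 11.4.4.4 summarises observed QTcF change by arm and time. Those data reflect all analytes together, though without a modelled 90% CI.

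It can be said, finally, that choosing the linear combination belongs in the analysis plan, which is not at hand and may settle it. That would hold if the protocol had left the output open. It fixed a formula instead, and the formula does not fit one of the permitted models. This part of the objection does not remove the point.

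**Conclusion.** The point holds conditionally. If FQ and SSR97213 enter as separate covariates, the stated rule gives only partial effects at peaks that may not coincide, and the protocol specifies no joint effect with a 90% CI for each dose group. The interval for the total cannot be rebuilt from the separate intervals and may be higher or lower than the FQ-only bound.

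The size cannot be established from the protocol. The illustration (5.28 ms, upper bound about 9.0 to 13.5 ms, against 3.52 and 9.74 ms for FQ alone) rests on an assumed metabolite share of one half, an equal relative SE, and slope correlations of -0.9 to 0.5. It also borrows placebo-corrected figures, whereas Section 11.4.5.3.4 predicts change from baseline. The protocol does not say whether SSR97213 was in the earlier model; if it was not, the FQ slope already carries some metabolite effect and the illustrated total counts part of it twice. No percentage of understatement should be quoted as a finding. The change is worth making because these figures are prepared for the DMC and the correction is cheap.

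**What to change.** In Section 11.4.5.3.4, state that when more than one analyte is in the model, the main prediction for each dose group is the sum, over all analytes in the model, of slope times geometric mean concentration at the same nominal time. Give it at each nominal time from T2h to T48h with samples for every analyte in the model, with pointwise 90% CIs from the joint covariance of the fixed-effect slopes, and highlight the time with the largest estimate. When the combined concentration is selected, report slope times combined Cmax. Keep the single-analyte terms as supporting output.

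Reconcile the synopsis, Section 11.4.5.3.2 (including the final-analysis paragraph), Section 11.4.5.3.4 and Section 11.4.5.3.5, so that each says which analytes its prediction covers and whether a CI is given.

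The cost is a set of extra estimate statements, one per time and dose group, in the planned PROC MIXED model. No new data are needed: Section 9.4.1 already matches FQ sampling to ECG times over the first 48 hours in Cohorts 1a and 1b, apart from T0.5h. The intervals are pointwise, so the interval at the highlighted time should not be presented as one for the maximum over time.
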